#### 7.3.4. Concomitant medication and care

Patients participating in the study will receive supportive treatment according to the IAP/APA evidence-based guidelines for the management of AP (2) as prescribed by the treatment-responsible physician. This includes supportive therapy with intravenous fluid therapy (Ringer's lactate 5-10 ml/kg per hour), enteral feeding (elemental or polymeric enteral nutrition formulations via nasojejunal or nasogastric route, alternatively parenteral if nasojejunal tube feeding is not tolerated) and analgesics. As the patients will be admitted during participation in the study, all concomitant medication and care will be registered in the patient's medical files as with any other patient and subsequently transferred to the CRF. This specifically includes a detailed quantification of the need for analgesics (separated into opioids and non-opioids) as this is of great clinical significance.

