### 7.4.2. Secondary endpoints

- Difference in daily **PASS scores** between subgroups
- Difference in daily assessments of circulating **pro- and anti-inflammatory markers** (including CRP, IL-6, IL-8, IL-18, TNF- $\alpha$  and CD163) as well as **intestinal barrier markers** between subgroups
- Difference in **intestinal permeability** between subgroups measured from 48 to 72 hours after randomization using the oral polyethylene glycol 400/4000 test
- Difference in **intestinal motility** assessed by means of gut/colon transit using a CT-based radiopaque marker method on day 5 (+/- 1 day) between subgroups
- Difference in **pancreatic complications** (e.g. edema, fluid collections and necrosis) assessed and quantified with contrast-enhanced CT on day 5 (+/- 1 day) after randomization (20)
- Difference between subgroups in the following **clinical outcome parameters**: pain intensity and gut function (assessed by questionnaires), quantification of analgesics (separated into opioids and non-opioids), need for nutritional support, disease severity, invasive treatments, intensive care and hospital stay, as well as mortality during total hospitalization
- Difference in **health resource utilization** during hospitalization between subgroups

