- ≥ 48 h of treatment, but discharge before day 5: Participant will be lost to follow-up on the following outcomes: daily PASS scores, blood samples, vital signs, quantification of need for analgesics, nutritional support, intravenous fluid resuscitation and antibiotics, and data will be analyzed using the Last-Observation-Carried-Forward method (see section 9.3.). The participant will be asked to complete questionnaires at home and they will be offered a follow-up CT scan in an outpatient setting on day 5 (+/- 1 day). Furthermore, they will be invited to participate in the 14-day follow-up and readmission rates as well as mortality will be registered retrospectively.

Randomization	Methylnaltrexone or placebo (0.15 mg/kg/day)				End of study	Follow-up
Baseline	24±2 hours	48±2 hours	72±2 hours	96±2 hours	120±2 hours	14±2 days
PASS	PASS	PASS	PASS	PASS	PASS	PASS
Clinical outcome	Clinical outcome	Clinical outcome	Clinical outcome	Clinical outcome	Clinical outcome	Clinical outcome
Blood samples	Blood samples	Blood samples	Blood samples	Blood samples	Blood samples	Blood samples
		Intestinal permeability		Intestinal transit time		

Computed tomography				Computed tomography	Health resource utilization
---------------------	--	--	--	---------------------	-----------------------------

**Table 1:** Participant timeline. PASS; pancreatitis activity scoring system.

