### 9.3. Statistical methods

A repeated measures linear mixed effects model will be used for the primary analysis and will include terms for treatment group, assessment time point (day after randomization), and the interaction of treatment with assessment time point. Summary statistics and trend curves of PASS scores will be provided for the individual time points, and the difference in PASS scores between groups 48 hours after randomization is considered the primary efficacy parameter. Subgroup and covariate analyses will be performed if applicable and in case differences in patient subgroups deemed clinically relevant are evident. The primary analysis will be by intention to treat and in case of early hospital discharge or other reasons for missing values, the Last-Observation-Carried-Forward method will be employed. Trends in PASS and other secondary endpoints assessed consequently during the treatment period (biochemical tests and clinical outcome parameters) are analyzed using linear random-effects models and results presented as fitted trend curves. Outcomes assessed at single time points (baseline characteristics, CT features and gut permeability) are compared using Student's t-test or non-parametric analysis for continues data as appropriate. Binary outcomes will be analyzed using Fisher's exact test. All secondary endpoints will be analyzed by per-protocol.

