6.3. Major Protocol Deviations

It is expected that a proportion of the patients included into the study, will recover before 5 days have passed and thus be discharged before completing the study protocol. In case of early discharge, data handling of both primary and secondary outcomes be stratified according to table 2:

< 48 hours of treatment	All data collection will be terminated upon discontinuation participant is regarded as dropout.
\geq 48 hours of treatment, but discharge before day 5	Participant will be lost to follow-up on the following outcomes: daily PASS scores, blood samples, vital signs. The participant will be asked to complete questionnaires at home, and they will be offered a follow-up CT scan in an outpatient setting on day 5 (+/- 1 day). Furthermore, they will be invited to participate in the 14-day follow-up and mortality will be registered retrospectively.

Table 2

For the statistical analyses, the Last-Observation-Carried-Forward method will be employed in case of early hospital discharge or other reasons for missing values. We expect most missing values to be a consequence of early discharge (~ recovering early from their disease) and thus the Last-Observation-Carried-Forward method will reflect this by carrying forward a value corresponding to low disease activity after discharge, which we find to be a fair assumption. If this is not the case, e.g. if a lot of missing values are due to severe disease, we will consider using other methods for imputation of missing values.

7. Implementation of Analysis Plan

A monitor will be allocated from the good clinical practice (GCP) unit at Aarhus and Aalborg University Hospitals, and the responsible monitor will contact and visit the principal investigator on a regular basis. The monitor will be authorized to inspect the different study records (CRFs,

Aalborg, Denmark

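### Protocol 7.5.1 carries in-hospital analgesic, nutrition, IV-fluid and antibiotic values past discharge by LOCF, and the SAP drops these variables without replacing the rule

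*Protocol*

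**What the plan says.** Protocol 7.5.1 sets a rule for patients who are ready to go home before five days of treatment are complete. One branch begins "≥ 48 h of treatment, but discharge before day 5: Participant will be lost to follow-up on the following outcomes". After PASS, blood samples and vital signs, its list ends with "quantification of need for analgesics, nutritional support, intravenous fluid resuscitation and antibiotics, and data will be analyzed using the Last-Observation-Carried-Forward method". Protocol 9.3 gives the general rule: "in case of early hospital discharge or other reasons for missing values, the Last-Observation-Carried-Forward method will be employed".

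Protocol 7.4.2 includes among its clinical outcome parameters "quantification of analgesics (separated into opioids and non-opioids), need for nutritional support, disease severity". It does not name IV fluids or antibiotics. Health resource utilization is a separate bullet, to be compared "during hospitalization between subgroups". On the data source, Protocol 7.3.4 says that "all concomitant medication and care will be registered in the patient's medical files as with any other patient and subsequently transferred to the CRF".

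Protocol 9.3.2 leaves missing-data handling to the final SAP. Table 2 in SAP 6.3 restates the early-discharge rule with a shorter list: "Participant will be lost to follow-up on the following outcomes: daily PASS scores, blood samples, vital signs". None of the four care variables is an outcome in SAP 2.2, SAP 2.3 or SAP Table 1; opioid use appears there only as an input to PASS. SAP 6.3 nevertheless keeps a general rule: "the Last-Observation-Carried-Forward method will be employed in case of early hospital discharge or other reasons for missing values". Its reason is that the carried value will represent low disease activity.

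Secondary endpoints are analysed per protocol (Protocol 9.3, SAP 2.5). SAP 2.5 requires more than 75 % of the study drug and no major protocol deviation.

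**The concern.** LOCF is a way of filling in values that nobody observed. In-hospital fluids and nutritional support after discharge are not unobserved: the patient has left and the amount is zero. If the last in-hospital record is above zero, LOCF replaces a known value with a false one. Analgesics and antibiotics differ, because they may continue at home. There the true value is unknown, but the last inpatient dose is a poor stand-in for it.

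The SAP's defence of LOCF concerns disease activity. It may suit a severity score. It says nothing about care delivered, since the last hospital day can still include fluids or opioids that stop when the patient leaves.

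The error need not cancel between arms. SAP 2.5 itself raises the possibility that methylnaltrexone patients are discharged earlier. The arm that goes home sooner would then collect more carried-forward care, which works against it on analgesic use and nutritional support.

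**Working it through.** **The plan's own figure.** The documents compute nothing on this point. Their one calculation, the sample size, reproduces: 2 x (1.960 + 0.842)² x (40/25)² = 40.2, rounded up to 41 per group. Nothing below depends on it.

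**Records that LOCF would fill.** Protocol Table 1 schedules assessments at 24, 48, 72, 96 and 120 hours. Discharge just after the 48, 72 or 96 hour record leaves 3, 2 or 1 records to fill.

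**Effect of the per-protocol rule.** SAP 2.5 gives no denominator for the 75 % threshold. Read against the planned 120 hours:
- 0.75 x 120 = 90 hours.
- Discharge at 48 hours (48/120 = 40 %) or 72 hours (72/120 = 60 %) removes the patient from the secondary analyses.
- Discharge after 90 but before 96 hours leaves the 96 and 120 hour records to fill.
- Discharge between 96 and 120 hours leaves the 120 hour record only.

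On this reading at most two records per patient are imputed.

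**Shift in the between-arm difference.** Let p be the share of an arm's analysed patients discharged early, k the mean number of carried days and v the last daily value. Relative to in-hospital use of zero after discharge, LOCF adds p x k x v to an arm's mean five-day total. If k and v are the same in both arms, the difference between arms shifts by

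(p_active - p_placebo) x k x v.

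None of p, k or v is in the documents. The values below are assumptions, with v = 2 L/day for IV fluid and 5 mg/day for IV morphine except in the first row.

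| Gap in early discharge | Carried days | Shift, IV fluid | Shift, IV morphine |
|---|---|---|---|
| any, with last value 0 | any | 0 | 0 |
| 0 points | any | 0 | 0 |
| 10 points | 2 | 0.10 x 2 x 2 = 0.4 L | 0.10 x 2 x 5 = 1 mg |
| 20 points | 1 | 0.20 x 1 x 2 = 0.4 L | 0.20 x 1 x 5 = 1 mg |
| 20 points | 2 | 0.20 x 2 x 2 = 0.8 L | 0.20 x 2 x 5 = 2 mg |

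These are shifts in the mean five-day total per patient. Per day, 0.8 L is 0.8/5 = 0.16 L and 2 mg is 2/5 = 0.4 mg. Under the 90 hour reading, two carried days is the maximum, so the last row is an upper case for that gap and those last values.

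**Primary endpoint.** This branch applies only after at least 48 hours of treatment, so the 48 hour assessment falls before the days that are filled.

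**The case against.** The strongest reply is that the SAP has moved on. Protocol 9.3.2 defers missing data to the SAP, whose Table 2 and outcome lists no longer contain the four variables. If no analysis of them is planned, there is nothing to bias. This reduces the reach of the point but does not dispose of it. Protocol 7.4.2 still names analgesics and nutritional support as secondary endpoints, the SAP does not say they were dropped, and its general LOCF sentence would apply if they were analysed.

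Second, patients fit for discharge may already have stopped fluids and opioids. That is true for some, and for them the rule does no harm. Nothing in the documents guarantees it, or says whether the last value covers the preceding 24 hours.

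Third, the per-protocol rule removes many early discharges. This stands for the 120 hour reading. SAP 6.3 also discusses early discharge under its heading on major protocol deviations, so a literal reader might exclude all these patients. Yet the same section says its table governs both primary and secondary outcomes, so the documents do not settle this.

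A reader might also infer that 7.5.1 contradicts the in-hospital window in 7.4.2. That is not shown. The window belongs to the health resource bullet, analgesics and nutritional support sit in another, and neither document says that health resource use is built from carried-forward days.

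**Conclusion.** The rule in Protocol 7.5.1 is wrong for in-hospital IV fluids and nutritional support whenever the last value is above zero, and unreliable for analgesics and antibiotics. Two of the four, analgesics and nutritional support, are named secondary endpoints.

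With similar carried days and last values in both arms, bias needs two conditions: last values above zero and unequal early discharge. It then runs against the arm discharged earlier. Its size cannot be derived from the documents. It ranges from zero to 0.8 L or 2 mg in the between-arm five-day total under the assumptions of a 20-point gap, two carried days, and 2 L or 5 mg per day. The fluid figure concerns a variable that neither document names as an endpoint.

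It would be tempting to conclude that the rule will hide or reverse a benefit of the drug. The documents do not support that: they give no discharge shares or last values, and the analysis set may exclude many of the patients concerned. What is established is a faulty imputation rule and an unreconciled difference between Protocol and SAP.

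**What to change.** Before unblinding, amend Protocol 7.5.1 and SAP 6.3 to say that LOCF does not apply to care and medication variables. Then:

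- Count in-hospital IV fluids and nutritional support as zero after discharge, unless home therapy is documented.
- Analyse analgesics (opioids and non-opioids) and antibiotics as in-hospital use over the fixed 0-120 hour window, and label them so. Use the discharge prescription only as a supplementary description, because it records what was prescribed and not what was taken.
- In the SAP, either list these variables as outcomes with their analysis or state that they were dropped from the Protocol's list.

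The cost is a wording change in two sections and slightly more analysis work. The sample size does not change.

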#### 7.6. Sample size

We calculated that 41 patients per group will be needed to detect a difference in the PASS score of 25 points with a within-group standard deviation of 40 points (22), 80 % power and a 2-sided alfa level of 0.05. Hence, the sample size is set at 45 patients per group to allow for possible dropouts.

#### 7.7. Recruitment

Patients admitted with AP will be identified and contacted by study personnel upon or during admission. Information regarding current and previous medical conditions will be passed on by the treatment-responsible physician from medical records to study personnel in order to identify eligible patients. This will be ensured by study personnel being in daily contact with the staff at the relevant departments at the respective inclusion sites with the purpose of monitoring the development of SIRS in patients with AP. This will be conducted in accordance to "Sundhedsloven § 46, stk. 1", under the responsibility of the primary investigator at the respective centers. AP is a relatively common disease and thus we expect approximately 10 patients to be admitted in total every week at our four inclusions sites. We expect at least half of these (i.e. 5) to be eligible for participation in the study.

#### 7.8. Information about the study

All patients will be informed both oral and written before they decide whether they want to participate in the study. Furthermore, they will be informed that they can withdraw from the study at any given time without giving a reason. The participants are also allowed to have an assessor with them to the interview. Competent delegated personnel (medical doctors affiliated with the study or trained site staff with GCP-authorization as well as knowledge and experience with the disease involved and conduction of clinical randomized placebo-controlled studies) will give the oral information interview according to the Research Ethics Committee's guidelines. The interview will take place in quiet surroundings at one of our respective inclusion sites. During the interview, the participant will be informed thoroughly about the purpose of the study, the specific procedures the study entails, and potential benefits and risks. Any questions the participant have, will also be answered here.

The written information (“Deltagerinformation”) is given to the participant upon contact. After the interview (see section 7.8.), where the participant has received information (oral and written), they are encouraged to consider whether they want to participate in the study or not before they sign the informed consent. As these patients are admitted with an acute condition the usual requirement of 24 hours for consideration before signing the informed consent is not deemed feasible. However, study personnel will ensure that patients will have sufficient time to consider participation before signing the informed consent. This includes adequate time to discuss with relatives in case the patient wishes to do so. In signing the informed consent, participants will be separately asked whether they want to contribute to the establishment of a biobank for both blood and urine samples. After the participant has signed the informed consent, they will be randomized to either active treatment (methylnaltrexone) or placebo (1:1) and receive an ID-number, which will be identical to the randomization-number. For more detailed information about informed consent and confidentiality see section 11.4.

## 8. Methods: Allocation of interventions

### 8.1. Allocation

Randomization will be conducted by the Hospital Pharmacy at Herlev Hospital in blocks of random size(block-randomization), using approved statistical software e.g. from the website [www.randomization.com](http://www.randomization.com). A specific randomization will be assigned by the Hospital Pharmacy to the individual patient once study personnel have completed inclusion. This randomization number will be returned to study personnel, which alongside with participants will be blinded to the allocation. None of the collected data are expected to unblind the randomization. Methylnaltrexone and matching placebo will be ordered at and delivered by The Hospital Pharmacy to the respective investigational sites. All medication will be labeled with the randomization number corresponding the allocation as well as the information that it is intended for use in a clinical trial only. All sites will have trained personnel to carry out a documented acceptance testing to ensure the right delivery and to keep a strict study medication account.

### 8.2. Blinding

The study is double-blinded, and the blinding will be conducted by the Hospital Pharmacy at Herlev Hospital. This way of blinding will ensure that personnel involved in the project and participants included in the study are prevented from knowing information that might lead to bias of the results. All study medication will be labelled indicating “study medication”, “id”, “initials”, “period”, “daily dosing paradigm” and “contact information”. Labelling will be performed by the Hospital Pharmacy at Herlev Hospital, according to Annex

13 of the Good Manufacturing Practice guidelines of the European Commission, ICH, GCP guidelines, and local law.

In case of an medical emergency (e.g. SUSAR, see section 10.2.3.) that necessitates knowledge of the treatment randomization, the individual treatment assignment for each subject will be available at each study center in sealed envelopes (provided by The Hospital Pharmacy) stored in a secure area accessible to study personnel allowed by the investigator to open the code for a single subject. The other study centers can always get in contact with the primary study center by a provided phone number in case of a situation where unblinding is necessary. This procedure allows unblinding of individual subjects, without revealing codes of the entire study. Thus, the study personnel will be able to determine which treatment a particular subject was given by opening the sealed envelope with the corresponding randomization number. The investigator must state the reason why the code was broken on the envelope, date and sign it.

A subject that discontinues will be asked about the reason(s) for discontinuation and the presence of any adverse events but are not obliged to provide this information. If needed, they will be seen and assessed by a medical doctor affiliated with the study. Dropouts will be replaced by new subjects and a mirror randomization will be performed i.e. they are part of the same randomization, but with a new number (e.g. 101 replaces 1 etc.).

Patients with AP will be admitted while participating in the study and hence have the study medication (Relistor® or matching placebo) administered to them by medical professionals. The medication and placebo will be delivered to the medical staff from the Hospital Pharmacy at Herlev Hospital in the form of fluid for infusion with similar appearance, so that the medical staff treating the patient will remain blinded.

## 9. Methods: Data collection, management, and analysis

### 9.1. Data collection methods

#### 9.1.1. Pancreatitis Activity Scoring System

PASS is a validated assessment tool for AP based on five clinical parameters, which are weighed according to figure 2 (23). It quantitatively evaluates the course of AP and has proven useful for monitoring disease severity as well as predicting clinical outcome in patients admitted with AP (22). Organ failure (i.e. renal, respiratory and cardiovascular) will be assessed according to the Modified Marshall scoring system as defined in the Revised Atlanta criteria (20). Thus, organ failure of the cardiovascular and renal system, is assessed by

means of systolic blood pressure and serum creatinine respectively. The ratio between partial pressure of oxygen in arterial blood ( $\text{PaO}_2$ ) and the fraction of inspired oxygen ( $\text{FiO}_2$ ) is used to assess the respiratory system. Not all participants included into this study are expected to have  $\text{PaO}_2$  values available. Thus, we will use the ratio between peripheral capillary oxygen saturation ( $\text{SpO}_2$ ) and  $\text{FiO}_2$  instead, as previous studies have shown that these two ratios correlate well (24,25).

### Pancreatitis activity scoring system

Clinical feature	Weight
Organ failure	100 per system
Intolerance to solid diet	0/40 (N/Y)
Systemic inflammatory response syndrome (SIRS)	25 per criteria
Abdominal pain	(0-10) x 5
Intravenous morphine equivalent dose (mg)	(1/mg) x 5

EXAMPLE: Patient with acute pancreatitis

Kidney failure, tolerant to solid diet, fulfills 1 SIRS criteria, scores abdominal pain 6, need of 20 mg intravenous morphine  
 $\text{PASS} = 100 + 0 + 25 + (6*5) + (20*5) = \underline{255}$

SIRS criteria
1. Body temperature $> 38^\circ\text{C}$ or $< 36^\circ\text{C}$
2. Heart rate $> 90/\text{min}$
3. Respiration $> 20/\text{min}$ or $\text{PaCO}_2 < 32\text{mmHg}$
4. White blood cell count $> 12.0 \times 10^9/\text{L}$ or $< 4.0 \times 10^9/\text{L}$

EXAMPLE: Patient with acute pancreatitis

Body temperature  $37.8^\circ\text{C}$ , Heart rate 120, Respiration 19/min  
White blood cell count  $18.0 \times 10^9/\text{L}$   
 $\text{SIRS score} = 0 + 1 + 0 + 1 = \underline{2}$

Figure 2: Pancreatitis Activity Scoring System (PASS)

